9.1.1 Adverse Events in the Double-Blind Treatment Period

TEAEs in the double-blind treatment period are defined as AEs with an onset date on or after the start of double-blind treatment. In more detail, TEAEs are all adverse events which started after start of double-blind IMP; or if the event was continuous from end of the single-blind placebo run-in period and was worsening, serious, study drug related, or resulted in death, discontinuation, interruption or reduction of study therapy. Adverse Events occurring up to 30 days after the last day of double-blind dosing will be included in the summary tables.

The incidence of AEs in the double-blind treatment period will be tabulated by treatment group and overall using the Safety Sample. Incidence of TEAE during the double-blind treatment period of at least 5% in either centanafadine group and also greater than placebo by SOC and MedDRA PT will be provided.

Unless otherwise specified, in general, analysis of safety data will be performed on observed case and for last visit.

SAP 405-201-00013

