3.2.2 Double-blind Treatment Period

Trial assignments for the double-blind treatment period will be made once eligibility is confirmed. Eligible subjects will be randomized in a 1:1:1 ratio at baseline (Visit 3) to one of the following 3 treatment groups:

- Centanafadine SR 200 mg TDD
- Centanafadine SR 400 mg TDD
- Matching placebo

Neither the investigator nor the subject will be aware of the treatment assignment after randomization. All doses of centanafadine SR and matching placebo should be taken orally BID and can be administered without regard to meals, and should be taken at approximately the same time each day, with the first dose taken in the morning. The second dose should be taken 4 to 6 hours after the morning dose is administered.

Subjects randomized to receive the target TDD of 200 mg centanafadine SR will start at the target dose on Day 1 of the double-blind treatment period and remain at that dose for the duration of the trial (Table 3.2.2-1). Subjects randomized to receive a TDD of 400 mg centanafadine SR will receive a TDD of 200 mg centanafadine SR on Day 1 of the double-blind treatment period for 7 days before they are escalated to their target TDD of 400 mg on Day 8 for the duration of the trial (Table 3.2.2-1).

Protocol 405-201-00013

Table 3.2.2-1 Dosing Schedule for Centanafadine SR Tablets			
Day(s)	Time	Total Daily Dose	
		200 mg Target	400 mg Target
1 through 7	2 tablets orally in morning	1 × 100 mg + 1 × PBO tablet	1 × 100 mg + 1 × PBO tablet
	2 tablets orally 4-6 hr later	1 × 100 mg + 1 × PBO tablet	1 × 100 mg + 1 × PBO tablet
8 and thereafter	2 tablets orally in morning	1 × 100 mg + 1 × PBO tablet	2 × 100 mg
	2 tablets orally 4-6 hr later	1 × 100 mg + 1 × PBO tablet	2 × 100 mg

PBO = placebo.

For subjects randomized to placebo, they will take 2 placebo tablets in the morning and 2 tablets in the afternoon for the duration of treatment.

Once the subject is at the target dose, further dose modification is not permitted. Dose modification is not allowed at any time during the trial.

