3.9 Screen Failures

A screen failure subject is one from whom informed consent is obtained and is documented in writing (ie, subject signs an eICF), but who is not randomized or assigned to trial treatment.

For this trial, treatment begins with the first dose of the IMP in the single-blind placebo run-in period. Subjects that have a positive alcohol test (via breathalyzer or blood), or positive drug screen for cocaine, or other illicit drugs (excluding marijuana) are not eligible to be retested or rescreened, and will be considered screen failures. Subjects that test positive for marijuana may be permitted to be enrolled if they have no evidence of a substance use disorder, and if they agree to refrain from use for the duration of the trial. Allowance for subjects testing positive for marijuana at screening require explicit approval from the medical monitor. Subjects that test positive for confirmed prescription use of ADHD medications at screening will be required to undergo a washout period (Section 4.1). If after the allotted washout period, a subject tests positive for ADHD medications prior to the start of the single blind placebo run-in period, subjects will be screen failed, and not permitted to rescreen. Screen failures previously excluded for a positive urine drug screen due to use of prescription or over-the-counter (OTC) medications or products not used for the treatment of ADHD, may be retested or rescreened for participation in the trial only with the explicit consent of the medical monitor. Subjects will be administered the ASRS prior to the start of the single-blind placebo run-in period, and those with a $\geq 30\%$ improvement in the (18-item) ADHD Symptoms score compared to the score at screening will be screen failed, and not eligible for rescreening. Screen failures excluded for any other reasons may be rescreened at any time if the exclusion characteristic has changed. In the event that a screen failure is rescreened a new eICF must be signed, a new screening number assigned, and all screening procedures repeated.

Protocol 405-201-00013

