- Pregnancies are also defined as IREs. Although normal pregnancy is not an AE, it will mandate IMP discontinuation and must be reported on an IRE form to the sponsor. Pregnancy will only be documented on the AE eCRF if there is an abnormality or complication.

Clinical Laboratory Test Value Changes: It is the investigator's responsibility to review the results of all laboratory tests as they become available. This review will be documented by the investigator's dated signature on the laboratory report. For each abnormal laboratory test result, the investigator needs to ascertain if this is an abnormal (ie, clinically significant) change from baseline for that individual subject. This determination, however, does not necessarily need to be made the first time an abnormal value is observed. The investigator may repeat the laboratory test or request additional tests to verify the results of the original laboratory tests. If this laboratory value is considered medically relevant by the investigator (subject is symptomatic, requiring corrective treatment or further evaluation), or if the laboratory value leads to discontinuation, or fulfills a seriousness criterion, this is considered an AE.

Severity: Adverse events will be graded on a 3-point scale and reported as indicated on the eCRF. The intensity of an adverse experience is defined as follows:

- 1 = Mild:** Discomfort noticed, but no disruption to daily activity.
- 2 = Moderate:** Discomfort sufficient to reduce or affect normal daily activity.
- 3 = Severe:** Inability to work or perform normal daily activity.

IMP Causality: Assessment of causal relationship of an AE to the use of the IMP is defined as follows:

- Related:** There is a reasonable possibility of a temporal and causal relationship between the IMP and the AE.
- Not Related:** There is no temporal or causal relationship between the IMP and the AE.

Protocol 405-201-00013

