9.1.2 Adverse Events in the Single-blind Placebo Run-in Period

Adverse Events in the single-blind placebo run-in period will be summarized for patients in the Safety Sample. AEs occurring up to 30 days after the last day of IMP in this period, but prior to the start of the double-blind treatment period, will be included in these summary tables. The incidence of adverse events in the single-blind placebo run-in period will be tabulated by the double-blind treatment patients receive in the double-blind treatment period.

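### SAP 9.1.1 gives two conflicting definitions of a TEAE, and the broader one counts unchanged placebo run-in events as double-blind TEAEs

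*SAP*

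**What the plan says.** SAP 9.1.1 opens with a rule based on onset: TEAEs are "AEs with an onset date on or after the start of double-blind treatment". The next sentence, offered as an elaboration, keeps that rule and adds a second route. An event is also a TEAE "if the event was continuous from end of the single-blind placebo run-in period and was worsening, serious, study drug related", or if it led to death or to stopping, interrupting or reducing study therapy. The items are joined by a single 'or', so any one is enough, and none is tied to a change after the first double-blind dose.

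Other passages decide which events can take the second route:

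- Protocol 3.9 states that "treatment begins with the first dose of the IMP in the single-blind placebo run-in period", so run-in placebo is IMP.
- Protocol 5.1 defines a related event as one where "There is a reasonable possibility of a temporal and causal relationship between the IMP and the AE". It does not separate run-in placebo from double-blind product.
- SAP 9.1.2 adds that "The incidence of adverse events in the single-blind placebo run-in period will be tabulated by the double-blind treatment patients receive in the double-blind treatment period".
- Protocol 7.5 and 7.5.1 list the TEAE summaries but do not define a TEAE. They leave the detail to the SAP, so nothing there overrides SAP 9.1.1.

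**The concern.** Take a subject whose nausea starts on Day -5 on run-in placebo, is rated related, keeps the same severity and resolves by Day 3. Under the opening sentence of SAP 9.1.1 this is not a TEAE. Under the elaborating sentence it is. The rating that admits it as a TEAE then also places it in the potentially drug-related TEAE tables (CT-8.3.1 and CT-8.3.2), although it began before any active drug was taken. It appears in the run-in AE table (CT-8.2.2) as well.

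The stake is the secondary objective, safety and tolerability against placebo. Two programmers could build different TEAE flags from the same paragraph. The broader flag reports as emergent on double-blind treatment events that were already present, unchanged, when it began. The SAP's other safety rules avoid this. New-onset QTc categories (9.4.1) require that the value was not present at baseline, and emergent suicidality (9.6) is judged against the last measurement before the first double-blind dose.

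**Working it through.** **Step 1: apply both sentences to a run-in event still ongoing at the first double-blind dose.**

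| Event carried over from run-in | Opening sentence | Elaborating sentence |
|---|---|---|
| Unchanged; not serious, not related, no action | Not a TEAE | Not a TEAE |
| Unchanged; rated related | Not a TEAE | TEAE, and drug-related TEAE |
| Unchanged; serious | Not a TEAE | TEAE |
| Worsens | Not a TEAE | TEAE |
| Leads to death or a treatment action | Not a TEAE | TEAE |

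The sentences disagree in four of the five rows. The last two rows are reasonable grounds for calling an event emergent, provided the change comes after the first double-blind dose. The second and third rows are the problem, because nothing has emerged.

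**Step 2: can a placebo event be rated related?** Yes. Protocol 3.9 makes run-in placebo IMP and Protocol 5.1 rates causality against IMP. Protocol 3.7.1.2 requires subjects to believe that randomized treatment starts at Visit 2, and Table 3.7-1 collects AEs at Visits 2 and 3.

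**Step 3: direction and size.** The plan states no TEAE rate or carry-over rate, so there is no figure to reproduce. Let p be the proportion of an arm with a TEAE by double-blind onset. Let q be the proportion with an unchanged carried-over event that is serious or related. If q is independent of p:

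- reported rate = p + q(1 − p), which is never below p;
- reported risk difference = (p_active − p_placebo)(1 − q), if q is the same in both arms.

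Equal q in expectation follows from Protocol 3.2.2, where "Eligible subjects will be randomized in a 1:1:1 ratio at baseline (Visit 3) to one of the following 3 treatment groups", which comes after the run-in.

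Illustration, with every input assumed: p = 60% active and 45% placebo, q from 0.5% to 5%.

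- q = 0.5%: active 0.60 + 0.005 × 0.40 = 60.2%; placebo 0.45 + 0.005 × 0.55 = 45.3%; difference 15.0 × 0.995 = 14.9 points.
- q = 5%: active 0.60 + 0.05 × 0.40 = 62.0%; placebo 0.45 + 0.05 × 0.55 = 47.8%; difference 15.0 × 0.95 = 14.3 points.

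If q = 0, nothing changes.

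**Step 4: chance imbalance.** With the planned 150 per arm, the share of subjects with a carried-over event differs between two arms with SD √(2q(1 − q)/150). That is 1.1 points at q = 1% and 2.5 points at q = 5%. It adds noise to the comparison but has no direction.

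**The case against.** Several points on the other side stand.

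- A reader might infer that the rule biases the comparison for or against centanafadine. The documents do not support this: run-in events precede randomization, so they are balanced in expectation. SAP 9.1 and 9.1.1 plan incidence by group, not risk ratios or tests.
- A reader might multiply guessed run-in rates into a number of spurious TEAEs per arm and set it against the 5% and 2% table cut-offs. The documents give neither the share with an ongoing run-in AE nor the share rated related. A share with any carried-over event is also not comparable with cut-offs that apply to each preferred term and further require incidence above placebo.
- The run-in is single-blind. The protocol requires subjects to be unaware of it and states investigator blinding for the period after randomization. Raters who know the product is placebo may rate few events as related, so q could be near zero.
- A reader might think the run-in exists to give safety a clean starting point. Protocol 2.1 gives a different purpose: excluding likely placebo responders.
- An event that persists for weeks on active drug may have been prolonged by it, so it is too strong to say that no carried-over event could be due to double-blind treatment.
- Appearing in both the run-in and double-blind tables is not an arithmetic error. These are separate period summaries and no pooled total is planned.

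The remaining arguments are weaker. The second sentence is presented as an elaboration and may well be the operative rule, but that decides which sentence a programmer follows; it does not make the two agree. An inclusive rule errs toward reporting, but reporting an unchanged event in the run-in tables loses nothing.

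**Conclusion.** The point holds as a defect of definition. SAP 9.1.1 classifies an unchanged run-in event that is serious or rated related in two ways, and no other passage settles which applies. Under the broader reading, placebo-onset events enter the double-blind TEAE tables, and those rated related also enter the drug-related ones.

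The effect can only be upward on absolute incidence. It is the same in all arms in expectation, and it shrinks the risk difference by no more than the factor (1 − q). Its size cannot be computed from the documents because q is not given. The figures above rest on assumed rates, on q being independent of the true TEAE rate, and on q being equal across arms. Efficacy, type I error and power are unaffected. The correction is worth making because the wording conflicts and the change is cheap, not because a distorted treatment comparison has been shown.

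**What to change.** Replace the two sentences in SAP 9.1.1 with one rule. A TEAE is an AE with onset on or after the first double-blind dose, or a run-in AE that after that dose increases in severity, newly becomes serious, or results in death or in discontinuation, interruption or reduction of double-blind IMP. Remove relatedness, and seriousness without a change after that dose, as stand-alone triggers for carried-over events. Report unchanged carried-over events in the run-in tables under SAP 9.1.2, and list separately any serious run-in event still ongoing at the first double-blind dose.

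The cost is one SAP sentence and one change to the TEAE flag. The downside is a slightly less inclusive TEAE count; the separate listing keeps ongoing serious events visible.

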9.1.2 Adverse Events in the Single-blind Placebo Run-in Period

Adverse Events in the single-blind placebo run-in period will be summarized for patients in the Safety Sample. AEs occurring up to 30 days after the last day of IMP in this period, but prior to the start of the double-blind treatment period, will be included in these summary tables. The incidence of adverse events in the single-blind placebo run-in period will be tabulated by the double-blind treatment patients receive in the double-blind treatment period.

9.2 Clinical Laboratory Tests

Summary statistics for routine clinical laboratory measurements will be provided. For The double-blind treatment period laboratory tests, change from baseline for the double-blind treatment period will be summarized by treatment group. Potentially clinically relevant results in laboratory tests will also be summarized.

9.2.1 Clinical Laboratory Tests in Double-Blind Treatment Period

Potentially clinically relevant laboratory measurement test results in the double-blind treatment period will be identified for the Safety Sample and will be summarized by treatment group and listed. Criteria for identifying laboratory values of potential clinical relevance are provided in [Appendix 2](#).

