13.	Subjects that have a positive alcohol test (via breathalyzer or blood), a positive drug screen for cocaine, or other illicit drugs (excluding marijuana). Subjects with a positive drug screen for confirmed prescription or OTC use of ADHD medications at screening will be required to undergo a washout period (Section 4). NOTE: Subjects that test positive for marijuana may be permitted to be enrolled if they have no evidence of a substance use disorder, and if they agree to refrain from use for the duration of the trial. Allowance for subjects testing positive for marijuana at screening require explicit approval from the medical monitor.
14.	Subjects with a known intellectual disability or clinical evidence of intellectual disability based on the opinion of the investigator.
15.	Subjects with insulin-dependent diabetes mellitus are excluded. Subjects with non-insulin-dependent diabetes mellitus may be eligible for the trial if their condition is stable as determined by satisfying ALL of the following criteria: 
 • Screening glucose (non-fasting) < 200 mg/dL. (If the non-fasting glucose is \geq 200 mg/dL, subjects must be retested in the fasting state. Fasting glucose must be \leq 125 mg/dL.), • Subject has been maintained on a stable regimen of oral anti-diabetic medication(s) for at least 28 days prior to screening or diabetes has been well-controlled by diet for at least 28 days prior to screening, • Subject has not had any hospitalizations within the 12 months prior to screening due to diabetes or complications related to diabetes, AND • Subject's diabetes is not newly diagnosed during screening for the trial.
16.	Subjects presenting with, or having a history of, uncontrolled hypertension (systolic blood pressure > 140 mmHg or diastolic blood pressure > 90 mmHg) or symptomatic hypotension, or orthostatic hypotension which is defined as a decrease of \geq 30 mmHg in systolic blood pressure or a decrease of \geq 20 mmHg in diastolic blood pressure after at least 3 minutes standing compared with the previous supine blood pressure, OR development of symptoms.
17.	Subjects with known ischemic heart disease or history of myocardial infarction, congestive heart failure (whether controlled or uncontrolled), angioplasty, stenting, coronary artery bypass surgery, or other serious cardiac problems that would place him/her at increased vulnerability to the sympathomimetic effects of a stimulant medication.

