18.	The following laboratory test and ECG results are exclusionary: 
 1) Platelets \leq 75,000/mm³ 2) Hemoglobin \leq 9 g/dL 3) Neutrophils, absolute \leq 1000/mm³ 4) AST > 2 \times upper limit of normal 5) ALT > 2 \times upper limit of normal 6) Creatinine \geq 2 mg/dL 7) HbA_{1c} \geq 7% 8) QTcF or QTcB > 450 msec for males or > 470 msec for females NOTE: In addition, subjects should be excluded if they have any other abnormal laboratory tests, vital sign results, or ECG findings which in the investigator's judgment are medically significant and that would impact the safety of the subject or the interpretation of the trial results. Tests with abnormal results should be repeated to ensure reproducibility of the abnormality before excluding a subject based on the criteria noted above.
19.	Subjects with hypothyroidism or hyperthyroidism (unless condition has been stabilized with medications for at least the past 90 days) or an abnormal result for free T4 at screening (free T4 is measured only if result for TSH is abnormal).

Protocol 405-201-00013

Table 3.4.3-1 Exclusion Criteria	
20.	Subjects receiving any of the prohibited medications within the specified period prior to the start of the single-blind placebo run-in period, or who would be likely to require prohibited concomitant therapy during the trial (Section 4).
21.	Subject has a history of prior exposure to centanafadine.
22.	Subject has a history of dermatologic adverse reactions secondary to any drug exposure or anaphylaxis (or some type of systemic allergic reaction) to any substance.
23.	Subject has participated in a clinical trial involving either an investigational medication or a non-medication intervention within the last 60 days prior to screening or has participated in more than 2 clinical trials involving either an investigational medication or non-medication intervention within the past year.
24.	Subject has previously been randomized in this trial and subsequently withdrawn.
25.	In the opinion of the investigator, subject has not derived significant therapeutic benefit from 2 or more ADHD therapies of 2 different classes (eg, amphetamine and methylphenidate, or amphetamine and atomoxetine) given with an acceptable dose and duration during adulthood (aged 18 or older). NOTE: If subject has not derived significant therapeutic benefit due to an inability to tolerate side effects, eligibility can be discussed on case-by-case basis with the medical monitor.

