Appendix 1 Criteria for Identifying Vital Signs of Potential Clinical Relevance

Variable	Criterion Value ^a	Change Relative to Baseline ^a
Heart Rate ^b	> 100 bpm < 50 bpm	≥ 10 bpm increase ≥ 10 bpm decrease
Systolic Blood Pressure ^b	≥ 140 mmHg < 90 mmHg	≥ 20 mmHg increase ≥ 20 mmHg decrease
Diastolic Blood Pressure ^b	≥ 90 mmHg < 60 mmHg	≥ 10 mmHg increase ≥ 10 mmHg decrease
Orthostatic Hypotension	≥ 30 mmHg decrease in systolic blood pressure or a ≥ 20 mmHg in diastolic blood pressure after at least 3 minutes of standing compared to the previous supine blood pressure.	Not Applicable (baseline status not considered)
Orthostatic Tachycardia	≥ 25 bpm increase in heart rate from supine to standing	Not Applicable (baseline status not considered)
Weight	-	≥ 7% increase ≥ 7% decrease

^a In order to be identified as potentially clinically relevant, an on-treatment value must meet the “Criterion Value” and also represent a change from the subject’s baseline value of at least the magnitude shown in the “Change Relative to Baseline” column.

^b As defined in “Supplementary Suggestions for Preparing an Integrated Summary of Safety Information in an Original NDA Submission and for Organizing Information in Periodic Safety Updates,” FDA Division of Neuropharmacological Drug Products draft (2/27/87).

SAP 405-201-00013

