Appendix 2 Criteria for Identifying Laboratory Values of Potential Clinical Relevance

Laboratory Tests	Criteria
Chemistry	
AST (SGOT)	≥ 3 x upper limit of normal (ULN)
ALT (SGPT)	≥ 3 x ULN
Alkaline phosphatase	≥ 3 x ULN
BUN	≥ 30 mg/dL
Creatinine	≥ 2.0 mg/dL
Uric Acid	
Men	≥ 10.5 mg/dL
Women	≥ 8.5 mg/dL
Bilirubin (total)	≥ 2.0 mg/dL
Creatine Phosphokinase (CPK)	> 3 x ULN
Hematology	
Hematocrit	
Men	≤ 37 % and decrease of ≥ 3 percentage points from Baseline
Women	≤ 32 % and decrease of ≥ 3 percentage points from Baseline
Hemoglobin	
Men	≤ 11.5 g/dL
Women	≤ 9.5 g/dL
White blood count	≤ 2,800/ mm ³ or ≥ 16,000/ mm ³
Eosinophils	≥ 10%
Neutrophils	≤ 15%
Absolute neutrophil count	≤ 1,500/ mm ³
Platelet count	≤ 75,000/ mm ³ or ≥ 700,000/ mm ³
Urinalysis	
Protein	Increase of ≥ 2 units
Glucose	Increase of ≥ 2 units
Additional Criteria	
Chloride	≤ 90 mEq/L or ≥ 118 mEq/L
Potassium	≤ 2.5 mEq/L or ≥ 6.5 mEq/L
Sodium	≤ 126 mEq/L or ≥ 156 mEq/L
Calcium	≤ 8.2 mg/dL or ≥ 12 mg/dL
Glucose	
Fasting	≥ 100 mg/dL
Non-Fasting	≥ 200 mg/dL
Total Cholesterol, Fasting	≥ 240 mg/dL
LDL Cholesterol, Fasting	≥ 160 mg/dL
HDL Cholesterol, Fasting	
Men	< 40 mg/dL
Women	< 50 mg/dL
Triglycerides, Fasting	≥ 150 mg/dL

SAP 405-201-00013

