- CT-8.7.3 Listing of Treatment-Emergent Adverse Events of Special Interests (AESIs) During the Double-Blind Treatment Period (Safety Sample)
- CT-8.8.1 Incidence of Treatment-Emergent Abuse Potential-Related Adverse Events During the Double-Blind Treatment Period by System Organ Class and MedDRA Preferred Term (Safety Sample)

SAP 405-201-00013

- CT-8.8.2 Incidence of Treatment-Emergent Abuse Potential-Related Adverse Events During the Double-Blind Treatment Period by System Organ Class and MedDRA Preferred Term and Severity (Safety Sample)
- CT-8.8.3 Listing of Treatment-Emergent Abuse Potential-Related Adverse Events During the Double-Blind Treatment Period (Safety Sample)
- CT-9.1.1 Listing of Deaths During the Double-Blind Treatment Period
- CT-9.1.2 Listing of Deaths During the Single-Blind Placebo Run-in Period
- CT-9.2.1 Listing of Serious Adverse Events During the Double-Blind Treatment Period
- CT-9.2.2 Listing of Serious Adverse Events During the Single-Blind Placebo Run-in Period
- CT-9.3 Listing of Discontinuations of Study Medication Due to Adverse Events During the Double-Blind Treatment Period
- CT-9.4 Listing of Adverse Events for Subjects Discontinued from Study Due to Adverse Events During the Double-Blind Treatment Period
- CT-10.1 Criteria for Laboratory Test Values with Potential Clinical Relevance
 - CT-10.2.1.1 Listing of Laboratory Test Values with Potential Clinical Relevance During the Double-Blind Treatment Period by Subject (Safety Sample)
 - CT-10.2.1.2 Listing of Laboratory Test Values with Potential Clinical Relevance During the Double-Blind Treatment Period by Test (Safety Sample)
 - CT-10.2.2 Incidence of Laboratory Test Values with Potential Clinical Relevance During the Double-Blind Treatment Period (Safety Sample)
 - CT-10.2.3.1 Mean Change from Baseline of the Double-Blind Treatment Period in Clinical Laboratory Test Results - Serum Chemistry (Safety Sample)
 - CT-10.2.3.2 Mean Change from Baseline of the Double-Blind Treatment Period in Clinical Laboratory Test Results - Hematology (Safety Sample)
 - CT-10.2.3.3 Mean Change from Baseline of the Double-Blind Treatment Period in Clinical Laboratory Test Results - Urinalysis (Safety Sample)
 - CT-10.3.1.1 Listing of Laboratory Test Values with Potential Clinical Relevance During the Single-Blind Placebo Run-in Period by Subject (Safety Sample)

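### For several laboratory criteria, the on-treatment incidence table counts abnormalities already present at baseline, which attenuates drug-placebo contrasts

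*SAP*

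**What the plan says.** SAP Section 9.2.1 sets the counting rule: "Potentially clinically relevant laboratory measurement test results in the double-blind treatment period will be identified for the Safety Sample". It refers to Appendix 2 for the limits and mentions no baseline status. The matching output in the table list of SAP Section 13 is CT-10.2.2, "Incidence of Laboratory Test Values with Potential Clinical Relevance During the Double-Blind Treatment Period (Safety Sample)".

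Appendix 2 gives absolute limits for most tests, for example for "Absolute neutrophil count" (1,500/mm³ or lower). Hematocrit is an exception, since it also needs a fall of at least 3 percentage points from baseline. Urine protein and urine glucose are defined only as an increase.

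Elsewhere the SAP uses baseline. Under footnote a of Appendix 1, a vital-sign value must meet the criterion "and also represent a change from the subject"'s baseline value of a stated size. Most ECG criteria in Appendix 3 work the same way, and the QTc onset categories in Section 9.4.1 require that the limit was not exceeded at baseline.

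The entry limits are in Protocol Section 3.4.3. Criterion 18 covers, among others, hemoglobin and "Neutrophils, absolute". Criterion 15 covers glucose in non-insulin-dependent diabetes ("Fasting glucose must be" 125 mg/dL or lower, on retest after a high non-fasting value).

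**The concern.** A subject can enter the trial legitimately with a value that Appendix 2 flags, keep that value unchanged, and be counted in CT-10.2.2. For such criteria the table reports how many subjects had the abnormality at any time on treatment. It does not report how many developed it.

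This makes a laboratory effect harder to see. Subjects abnormal from the start add the same expected amount to each arm, so the arms look more alike than the new-onset rates would. The table is part of the evidence for the secondary objective on safety and tolerability, and a reader will take its title at face value.

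**Working it through.** **Step 1. Is there a planned figure to reproduce?** No. Neither document gives a baseline frequency of laboratory abnormality, an expected on-treatment rate, or a test for this table.

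**Step 2. Compare entry limits (Protocol 3.4.3) with relevance limits (SAP Appendix 2).**

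| Test | Excluded at entry | Flagged on treatment | Eligible and already flagged |
|---|---|---|---|
| Neutrophils | ≤ 1000/mm³ | ≤ 1500/mm³ | > 1000 to 1500 |
| Hemoglobin, men | ≤ 9 g/dL | ≤ 11.5 g/dL | > 9 to 11.5 |
| Hemoglobin, women | ≤ 9 g/dL | ≤ 9.5 g/dL | > 9 to 9.5 |
| Fasting glucose | > 125 mg/dL, only for diabetics retested after a non-fasting value ≥ 200 | ≥ 100 mg/dL | 100 to 125 in retested diabetics; no numeric fasting limit for others |
| Cholesterol, LDL, HDL, triglycerides | no numeric limit | absolute limits | any flagged value |
| AST/ALT | > 2 × ULN | ≥ 3 × ULN | none |
| Creatinine | ≥ 2 mg/dL | ≥ 2.0 mg/dL | none |
| Platelets, low | ≤ 75,000/mm³ | ≤ 75,000/mm³ | none |

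There is also no numeric entry limit for CPK, uric acid, eosinophils, white cells, BUN, bilirubin or alkaline phosphatase.

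**Step 3. Model the count.** Let p0 be the share meeting a criterion at baseline, s the share of these still meeting it on treatment (equal across arms), and a and b the new-onset rates on placebo and drug among the rest.

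- Placebo rate in the table = p0·s + (1 − p0)·a
- Drug rate in the table = p0·s + (1 − p0)·b
- Difference = (1 − p0)·(b − a), whatever the value of s

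**Step 4. Put numbers in.** All rates are assumptions, with a = 5% and s = 1.

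| p0 | b = 10%: table rates | Difference | Ratio | b = 15%: table rates | Difference | Ratio |
|---|---|---|---|---|---|---|
| 0 | 5.0% v 10.0% | 5.0 | 2.00 | 5.0% v 15.0% | 10.0 | 3.00 |
| 10% | 14.5% v 19.0% | 4.5 | 1.31 | 14.5% v 23.5% | 9.0 | 1.62 |
| 20% | 24.0% v 28.0% | 4.0 | 1.17 | 24.0% v 32.0% | 8.0 | 1.33 |
| 30% | 33.5% v 37.0% | 3.5 | 1.10 | 33.5% v 40.5% | 7.0 | 1.21 |

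Differences are in percentage points. Example: with p0 = 10% and b = 10%, 0.10 + 0.90 × 0.05 = 0.145 and 0.10 + 0.90 × 0.10 = 0.190, so the ratio is 1.31.

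Lower persistence softens the ratio but not the difference. With s = 0.7, p0 = 20% and b = 15%, the table shows 18.0% v 26.0%, a difference of 8.0 points and a ratio of 1.44.

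**Step 5. Gauge visibility.** No test is planned, so power serves only as a yardstick. Take n = 150 per arm (Protocol 7.1), two-sided 0.05, and power = Φ{[|Δ|√n − 1.96√(2p̄(1 − p̄))] / √[r₁(1 − r₁) + r₂(1 − r₂)]}, where r₁ and r₂ are the two rates, p̄ their mean and Δ their difference. For a = 5%, b = 15%, s = 1:

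- p0 = 0: 0.83.
- p0 = 10%: 0.51 from the table's count; 0.79 among the 135 per arm not abnormal at baseline.
- p0 = 20%: 0.34 from the table's count; 0.74 among the 120 per arm not abnormal at baseline.

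**The case against.** The strongest reply is that other outputs already show what is missing. SAP Section 9.2.3 and CT-10.3.2 apply the same limits to the placebo run-in by later treatment group. By-subject listings exist for both periods, and mean changes from baseline are tabulated by arm. This stands in part: a reader can see pre-treatment rates per arm and could trace individuals by hand. But the run-in table is not linked subject by subject to the on-treatment table, and a mean change does not say how many subjects crossed a limit. Nor can the run-in rate simply be subtracted. Under Protocol Section 3.7.5.2, earlier samples need be fasting only where possible, while Day 42/ET must be fasting, so glucose and lipid criteria may be less assessable before dosing.

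A second reply is that baseline-free criteria can be deliberate: Appendix 1 sets baseline aside for orthostatic hypotension and tachycardia. That is fair, so the vital-sign comparison holds for most criteria, not all. No reason is given for the laboratory limits, however, and within one appendix hematocrit needs a change while hemoglobin does not.

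Third, entry is also narrowed by investigator judgment and by the need for medical monitor permission after a clinically significant screening result. This lowers p0 by an unknown amount but sets no limit for these tests.

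A reader might go further and infer that the laboratory analysis ignores baseline altogether, or that every drug signal is diluted. The documents do not support this. Hematocrit and the two urinalysis criteria are change-based. AST/ALT, creatinine and low platelets have no overlap at screening, and potential liver injury has its own table (SAP 9.2.2).

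**Conclusion.** The point holds for Appendix 2 criteria that have no change component and that eligibility does not screen out, notably neutrophils, hemoglobin, fasting glucose and lipids. For these, CT-10.2.2 is an any-occurrence count under an incidence title.

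The consequence is attenuation. The risk difference falls by the factor 1 − p0, and the ratio by more. The size rests on assumed p0, new-onset rates and persistence, and on persistence being equal across arms. It will vary by test: the overlap for hemoglobin in women is only half a gram per deciliter, while lipids have no entry limit.

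A reader might infer that the table favors the drug, or that the safety objective cannot be met. Neither follows. Randomization balances pre-existing abnormalities in expectation, the table is descriptive, and the safety assessment also rests on adverse events, vital signs, ECGs, suicidality and withdrawal data. The change is worth making because it yields a treatment-emergent rate from data already collected.

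**What to change.** Keep CT-10.2.2 and the listings as an any-occurrence summary. Add to SAP Section 9.2.1 and to the table list in Section 13, for the Appendix 2 criteria without a change component that overlap eligibility:

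1. **A treatment-emergent summary by arm.** Numerator: subjects who meet the criterion on treatment but not at the double-blind baseline, which SAP Section 7.1 already defines. Denominator: subjects who do not meet it at baseline and have at least one on-treatment value.
2. **A shift table of baseline against worst on-treatment value.** Replacing the existing count with new onset alone would lose subjects abnormal at baseline who then worsen, for example an eligible neutrophil count of 1400 falling to 600. The shift table keeps them visible.
3. **A rule for fasting criteria.** Use the last fasting pre-dose sample, and show subjects without one in a separate baseline-missing row.

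The cost is SAP wording, one added programming condition and one or two extra tables, with no new data. Denominators will vary by test, and not always slightly: at p0 = 30% the denominator is 30% smaller.
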